### 7.4.4. Photography methods

The digital photographs of each lymphatic malformation in this study will be acquired by the site investigators. The investigators will be fully trained in the standardized acquisition procedures. At least two digital photographs of the lymphatic malformation will be acquired for each subject at the baseline visit and the 20 week visit. Photographs may be taken at other visits but they will not be part of the final analysis. The first photograph will be taken with the image plane parallel to the lymphatic malformation (front-on view) and the second photograph will be taken with the image plane at a different angle to that of the first photograph (side-on view) so that the thickness of the lesion can be clearly visualized. The subject will be sitting on a chair while photographs are taken. If subject is an infant, subject's parent or guardian will be sitting on a chair with the infant sitting on his/her knees, if possible, or in his/her arms. In the field of view, all photographs will include a color chart for color and size calibration. Patient identification information, date of the photograph and therapy information will not be visible on the photograph. For each photograph acquisition, the color chart will be held in the same plane as the lymphatic malformation. The photographs will be acquired at a fixed distance from the patient at two different angles defined at baseline (one for Photograph 1 and one for Photograph 2).

The photographs will serve the following purposes:

- 1: To identify the lymphatic malformation or malformations if the subject has more than one malformation.
- 2: To qualitatively assess lymphatic malformation evolution between visits and to quantify the size and the color of the lymphatic malformation at baseline and Week 20.

#### 7.4.5. Laboratory tests

The CBC and chemistry panel is detailed in Appendix 17. These are to be assessed at the Screening Visit and End of Treatment Visit (Week 20). All required lab tests must have been completed. At the discretion of the PI or designee, a topical lidocaine-based anesthetic (eg. Lidocaine 4% cream) may be used prior to clinical laboratory sample collection to decrease potential discomfort to the subject. A pregnancy test will be done at the end of treatment for females of childbearing potential.

### 8. DATA MANAGEMENT PLAN

Paper source documents will be prepared prior to study start. These source documents will be used in clinic to collect data for the study. Data will be collected at study visits, using the prepared data collection forms. All source documents will be retained in the subject's study binder. Source documents can include, but are not limited to:

- Signed informed consent documents
- Data collection forms (source documents)
- Laboratory reports
- MRI reports
- Dictations/summary reports

REDCap, an electronic data capture (EDC) system, will be utilized in this study as an electronic case report form (eCRF). REDCap is a HIPAA-secure database system available through Stanford at <http://redcap.stanford.edu>. This system can only be accessed by authorized users, and only users with permission to view identifiers will be able to view PHI. Users must sign into REDCap using their Stanford University ID and password. Additionally, users may only access the database from a Stanford IP address, or via a Virtual Private Network (VPN). Prior to study start, a database will be designed for this study that incorporates the data points collected in the source documentation. The Stanford site will receive a copy of the paper source documents from the local cooperating research sites after every visit of the subject at the local site. The Stanford site will place the information from the local site into REDCap.

After each study visit, data will be transcribed from paper source documents into the electronic data capture (EDC) REDCap system. Hard copies of source documentation will also be retained and stored in the subject binder. Photographs, laboratory reports, and dictations will be uploaded to REDCap.

Study staff will be responsible for “cleaning” the source document data and EDC prior to monitoring at each site. This includes but is not limited to: making sure that dates are

logical, reasons for concomitant medication have a corresponding adverse event, making sure that GCP is followed, etc.

At monitoring visits at Stanford, the study monitor will verify that the data entered into REDCap matches the data recorded in the source documentation. REDCap data will be printed and the monitor will verify that this information is the same as in the source documentation.

Data from REDCap will be exported to excel, SPSS, or SAS for analysis. When exporting data, PHI will not be included in the dataset.

## **9. DATA SAFETY MONITORING BOARD**

A DSMB will be developed to monitor the study. The details of the DSMB are described in the Safety Monitoring Plan (SMP), in Item 10, section 2 of the IND application. The independent DSMB will assure that this trial is performed to the highest scientific and ethical standards. Prior to the start of the study, the DSMB will review the Clinical Protocol, Safety Monitoring Plan, Informed Consent forms, and proposed DSMB-specific reporting forms. Once the study has started, the DSMB will evaluate the scientific progress and safety of the trial, consider outside information that is relevant to the study, review proposed changes to the Clinical Protocol, ensure data integrity, ensure confidentiality of trial data and monitoring results, and make recommendations to the PI regarding the trial. The DSMB will meet prior to the start of the trial and then at least twice annually until 1 year after the last subject completes the last Week 32 or Week 32-A visit. Ad hoc or emergency meetings will occur as needed and the procedures for planning those meetings are described in detail in the Safety Monitoring Plan.

## **10. STATISTICAL DESIGN**

### **10.1. EVALUABILITY**

All subjects who receive study medication will be evaluable for the safety analysis. All subjects who receive study medication will be evaluable for the intent-to-treat analysis.

### **10.2. EFFICACY**

All subjects who receive study medication will be evaluated for efficacy.

#### **10.2.1. Primary Efficacy**

Summary statistics will be determined for change in lesion volume by a radiologist blinded to the time of the MRI and whether the patient was on treatment or placebo. The initial MRI will be compared to the MRI after 20 week of sildenafil or placebo. If the subject on placebo elects to take sildenafil for 20 weeks the MRI used for comparison after 20 weeks of sildenafil will be the MRI taken after 20 weeks of placebo.

We will include in the interim analysis information about the characteristics of LMs. We will do a sub-analysis looking at specifics of location, lesion type (microcystic, macrocystic, or mixed and percent macrocystic), as well as previous procedures, infections or other interventions. If this process documents characteristics of lesions that do or do not respond to sildenafil, we will reconsider our study entry criteria and submit a protocol amendment for the IND and this grant, focusing more on specific characteristics of which type of lesion a subject should have in order to be enrolled in the trial.

#### **10.2.2. Secondary Efficacy**

The secondary efficacy variables will be change from baseline and at visits four weeks twelve weeks, twenty weeks and 32 weeks.

These will include the changes in the soft tape measurements of the lesion by comparing the measurements of length, width, and hemispheric measurement. The volume of the lymphatic malformation will be estimated based on these measurements.

Statistical analysis of the *Subject's Assessment of Lymphatic Malformation Change* form. This will give data on the subject's evaluation of the change in lesion clinical characteristics from baseline, such as decreased discomfort, texture or thickness, distortion of normal anatomy or overall change by correlating the data obtained in the subject's completion of *Subject's Assessment of Lymphatic Malformation Change* form.

Statistical analysis of the *Lymphatic Malformation Assessment* form for each LM site. This will give data on the physician's evaluation of the lesion clinical characteristics on the days of the visits. This includes color, tenseness and texture, superficial component, deep component, and distortion of anatomical landmarks.

Statistical analysis of the *Lymphatic Malformation Assessment of Change* form for each LM site. This will give data on the physician's evaluation of the change in lesion clinical characteristics from baseline, such as change in texture or thickness, change in distortion of normal anatomy, and over change in lesions.

Change in LM volume from MRI assessments in relation to BSA will also be carried out. REDCap calculates the BSA from height and weight measurements at each visit. Since growth can be non-linear, relating the LM volume to a subject's BSA may help to explain why a small change to the LM (by MRI volume analysis) is assessed as moderate by the investigator and parents of the subject (i.e., the LM may have stayed the same size but the child grew quickly, so the LM appears smaller by visual assessment).

The digital photographs of each lymphatic malformation in this study will be acquired by the site investigators. At least two digital photographs of the lymphatic malformation will be acquired for each patient at each scheduled study visit, a front-on view and a side-on view. See Section 7.4.4. The clinical photographs evaluated by blinded observers in a blinded manner by physicians not associate with this trial. The observers of the

photographs will compare the baseline photographs and score the additional visits as worse, no change, 1-25%, 26-50%, 51-75%, 76-100% improvement. We will also examine the potential value of 3D photography during the Baseline, 20 Week and 20-A Week visit.

Presence, frequency or absence of infection during trial will be documented.

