receive active sildenafil to one placebo treated subject. During the twenty week evaluation visit, after completion of all evaluations, the randomization code will be broken and both the subject and investigator will know the results. The subjects who have randomized to placebo will have the option to begin a twenty week course of sildenafil. If the subjects who were on placebo elect to take active drug, the initiation visit can be completed at that time. The subject will then be followed with clinic visits at weeks 4, 12, 20 and 32 as indicated in the protocol. We will call the subjects at weeks 2, 8 and 16 to inquire about any questions that the subjects may have or any concerns. We will also request information on medication taken and their progress.

The subject's LMs will be categorized by the Pediatric Radiologist by the percent of the LM that is microcystic. Upon completion of the initial 15 subjects, the data will be evaluated in an interim analysis in order to determine if the percent of macrocystic component of the lesions suggests which subjects may have the best benefit. The initial 15 subjects will also be evaluated related to previous procedures, infections and other complications related to their lymphatic malformations. If specific characteristics of the LM are identified that suggests beneficial effect of the sildenafil, the protocol will be changed to enroll those subjects who are projected to have the best benefit. A new power analysis will be done to project the minimum numbers of subjects that should be enrolled further in the study.

Duration of Treatment: 20 weeks. Placebo subjects will complete 20 weeks of placebo and then have an option for 20 weeks of active sildenafil.

Duration of Assessment: The subjects will be evaluated for 20 weeks on therapy then followed for 12 weeks off therapy.

Open Label Extension: Placebo subjects will have an option to enter an open label treatment after they have completed 20 weeks of placebo.

Duration of treatment: Placebo 20 weeks  
Washout Between Periods: none  
Duration of Treatment: 20 weeks on active drug

After the completion of 20 weeks of sildenafil and 12 weeks of follow up, the subjects will have the option to be followed through an IRB approved long-term follow up trial not

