covered in this IND application. That IRB trial would allow up to five years follow up on subjects and would only allow investigators to observe how the subject is doing long term, whichever treatment options the subject pursues in consultation with their regular doctor in that time. That planned follow up protocol will allow Stanford to contact the subjects several times a year in order obtain information about any therapy they may elect to follow, including sildenafil if their regular doctor prescribes it, and their response to any therapy.

Multi-Center:

Yes

Number of Centers:

Up to 4

Blinding:

|                |     |
|----------------|-----|
| Observer-Blind | Yes |
| Subject-Blind  | Yes |
| Double-Blind   | Yes |

Randomization:

Group Assignment Ratio: 2:1 randomization of two subjects who receive sildenafil to one subject who receives placebo.

Concurrent Control:

No other treatments for lymphatic malformation will be allowed except antibiotics and/or surgical drainage if the lesions become infected. Treatment for recurrent infections in the lymphatic malformation will be allowed and documented during the trial. Concurrent medications will be documented. Subjects who require sclerosing agents or excisional surgery of their lymphatic malformation will be withdrawn from the trial.

Variable(s): PRIMARY: Change in lesion volume over twenty weeks of the test medication as evaluated by MRI examination. Comparison of placebo to sildenafil treated subjects.

SECONDARY: Change in lesion volume estimated using a soft tape measure to measure the length, width, and hemispheric measurement of each of the lymphatic malformations. (Berk, Berk et al. 2011) Completion of the form *Lymphatic Malformation Measurements*.

Subject's evaluation of the change in lesion clinical characteristics from baseline to 20 weeks by examining decreased discomfort, texture or thickness, distortion of normal anatomy or overall change obtained in the subject's

completion of *Subject's Assessment of Lymphatic Malformation Change* form.

Physician's evaluation of the lesion clinical characteristics on the day of the visit. This includes color, tenseness and texture, superficial component, deep component, and distortion of anatomical landmarks. This requires completion of the *Lymphatic Malformation Assessment* form for each LM site.

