beginning medication. Subjects local to Stanford will be seen at Stanford for all visits. Subjects local to other cooperating study sites will be seen at Stanford for Screening, Initial Dose Visit, and Week 20, and at their local cooperating research study site for Week 4, Week 12, and Week 32. These subjects will also be given the option to have their Week 20 eye and hearing exams done at the cooperating research study site or at Stanford. Laboratory tests will be conducted at Stanford for baseline and follow-up. The Stanford site will contact the subject by phone at 2 weeks, 8 weeks and 16 weeks. Subjects who received placebo during the first 20 weeks of evaluation will have the option at the twenty-week visit of commencing use of the active drug for the next twenty weeks. If the subject who initially received placebo decides that they do not want to receive sildenafil for 20 weeks they will then complete the data collected at the 32 week visit in addition to the 20 week visit. The subject will not need to return for the 32 week visit. If the subject who initially received placebo selects to start the medication they will then be seen at the 4 week, 12 week and 20 week visit after commencing medication. Subjects local to other cooperating research study sites will attend the Week 4, Week 12, and Week 32 visits at their local site and Week 20 at Stanford. The medication will be stopped after the 20 week visit and the subject will be seen at Week 32, having been off medication for 12 weeks. The subject will have an additional MRI done at Stanford at the completion of the twenty weeks of active medication. Subjects on placebo who elect to receive the active drug will have three MRI examinations. Subjects on active medication will be requested to stop the medication in order to be followed over the next twelve weeks with no medication (week 32).

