9. Completion of the physician's evaluation of the lesion clinical characteristics on the day of the visit. This includes color, tenseness and texture, superficial component, deep component, and distortion of anatomical landmarks. This requires completion of the *Lymphatic Malformation Assessment* form for each LM site.
10. Physician's evaluation of the change in lesion clinical characteristics from baseline, such as change in texture or thickness, change in distortion of normal anatomy, and over change in lesions. This requires completion of the *Lymphatic Malformation Assessment of Change* form for each LM site.
11. Collect study drug and perform compliance assessment; medication journal reviewed.
12. Obtain a pregnancy test if the subject is has achieved menarche.
13. The participant or parent/guardian and the investigator will complete the qualitative assessment of efficacy. The subject's evaluation of the response to the treatment will be reviewed. The results report of the MRI done at the twenty week visit will be shared with the subject and compared with the initial MRI reported results. After that discussion the subject will be told if they were on sildenafil or placebo. Subjects who received placebo will be given the option to start the sildenafil. Subjects who received active medication will be requested to stop the sildenafil for the next twelve weeks and follow up at the 32 week visit to examine the response of the lesion off of the sildenafil.

14. If subject received placebo and decides to receive sildenafil at this time, the study medication dose will be calculated and obtained from the pharmacy for adequate study medication to last until the next visit in 4 weeks. The 2 hour monitoring will be completed after the first dose as described in Baseline visit. For more detail, see Section 7.1.7. If the subject was on placebo and elects not to start sildenafil they will not need to return for the 32 week evaluation.
15. If the subject received placebo and decides to not receive sildenafil they will end the study at this time and complete additional information needed for the End of study 32 week visit described in 7.1.7. below.
16. If a subject approves, we will send a copy of the dictated record for the study visit to their local primary care doctor and /or pediatric dermatologist so that the physicians in their home community are aware of the study and the subject's participation in the study.

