**7.1.7. End of Study 32 weeks [ $\pm$  2 Weeks] at subject's cooperating research site or at Stanford if the subject is local to Stanford for subjects who are on active sildenafil for the initial twenty weeks of the trial**

1. Query subject and/or caregiver regarding any changes in general health and the use of concomitant medications. Obtain demographic information and review interim medical history, including information on all medications currently being taken. Review previous concomitant medications and current concomitant medications. Instruct the subject and/or caregiver of the excluded medications and give them a list if they do not have their list with them.
2. If any adverse events are observed or reported, they must be recorded as instructed in Section 13, Adverse Events.
3. Perform a physical examination including heart and pulmonary auscultation, liver and spleen palpation, abdominal auscultation and palpation, and documentation of peripheral pulses. Examine and describe the characteristics of their lymphatic malformation.
4. Obtain Vital Signs including height, weight, temperature, heart rate, blood pressure, respiratory rate, and oxygen saturation.
5. Clinical assessment of each lymphatic malformation including measuring the hemicircumference of the lesion by using a soft measuring tape placed on the skin over the area of the widest diameter of the lesion. The length, and width, will then be calculated as describe in Figure 2 of Berk et al (2011). In order to document the site of the measurements a diagram will be drawn by hand or photographs will be taken of the methods. Each clinic visit will try to duplicate the measurements methods used in the initial visit.

6. Completion of subject's evaluation of the change in lesion clinical characteristics from baseline, such as decreased discomfort, texture or thickness, distortion of normal anatomy or overall change obtained in the subject's completion of *Subject's Assessment of Lymphatic Malformation Change* form.
7. Completion of the physician's evaluation of the lesion clinical characteristics on the day of the visit. This includes color, tenseness and texture, superficial component, deep component, and distortion of anatomical landmarks. This requires completion of the *Lymphatic Malformation Assessment* form for each LM site.

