### 7.4.3. Lymphatic malformation assessment

The most precise method of lymphatic malformation evaluation will be the MRI examination. Clinical assessment of each lymphatic malformation includes measuring the hemicircumference of the lesion by using a soft measuring tape placed on the skin over the area of the widest diameter of the lesion. The investigators will be fully trained in the standardized methods to obtain these measurements. We have found in our preliminary subjects that the investigators vary in their measurement of length, width and hemispheric measurement unless they practice these measurements together in order to standardize their methods. The length, and width, will then be calculated as described in Figure 2 of Berk et al.(Berk, Berk et al. 2011) We will use linear mixed model to compare the changes in volume over time between and within subjects who receive placebo and those who receive sildenafil. In order to document the site of the measurements a diagram will be drawn by hand or photographs will be taken of the methods. Each clinic visit will try to duplicate the measurements methods used in the initial visit.

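### Does listing week 32 as a secondary efficacy visit commit the trial to a between-arm comparison that has no untreated placebo values?

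*Combined protocol and SAP*

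**What the plan says.** Section 10.2.2 sets the timing of the secondary variables in one sentence: "The secondary efficacy variables will be change from baseline and at visits four weeks twelve weeks, twenty weeks and 32 weeks". No arm is named. The only modelling statement is in section 7.4.3, in the paragraph on tape measurement: "We will use linear mixed model to compare the changes in volume over time between and within subjects who receive placebo". The other group in that comparison is the sildenafil arm. The statement does not say which visits enter, which comes last, or how time is coded.

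Other sections say who is seen at week 32 and why:

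- The heading of section 7.1.7 confines the initial-period visit to a site appointment "for subjects who are on active sildenafil for the initial twenty weeks of the trial".
- Section 7.1.6, step 13, gives its purpose: these subjects stop the drug and "follow up at the 32 week visit to examine the response of the lesion off of the sildenafil".
- Placebo subjects who decline sildenafil do not return. Section 7.1.6, step 15, says "they will end the study at this time and complete additional information needed for the End of study 32 week visit". Section 6.1 says "they will then complete the data collected at the 32 week visit in addition to the 20 week visit".
- Placebo subjects who accept start active drug at week 20. The synopsis records "Washout Between Periods: none". Their later visits carry an -A suffix in Table 16-1.

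The synopsis gives a shorter time frame for one secondary variable: "Subject's evaluation of the change in lesion clinical characteristics from baseline to 20 weeks".

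**The concern.** Read together, sections 10.2.2 and 7.4.3 seem to allow a between-arm model of tape volume that runs to week 32. By then the sildenafil arm is off drug and unblinded, and no placebo subject is still under observation and untreated. One arm would mix on-drug and off-drug visits while the other stopped at week 20.

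The section 6.1 sentence about decliners adds a second worry. Taken literally, a measurement made at week 20 could be stored as a week-32 value.

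At stake would be the reading of the tape-volume result and, if they are compared between arms, the two physician forms. The primary MRI comparison and the MRI volume relative to body surface area use the week-20 scan, so neither is exposed.

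**Working it through.** The plan gives no effect size, standard deviation or power, so there is no stated figure to reproduce. The check covers who can supply data, when, and what a model would do with them.

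**Who can supply a week-32 value.** Allocation is 2:1 (synopsis). Section 5.1 gives a goal of 40 completers and up to 60 enrolled.

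| Total | Sildenafil (× 2/3) | Placebo (× 1/3) | Untreated placebo scheduled at week 32 |
|---|---|---|---|
| 40 | 26.7 | 13.3 | 0 |
| 60 | 40 | 20 | 0 |

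The scheduled post-baseline tape visits are weeks 4, 12, 20 and 32 for sildenafil, and weeks 4, 12 and 20 for untreated placebo. Three of four are shared.

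**Timing.** The week-20 window is ±21 days in section 7.1.6, so it runs from 20 − 3 = 17 to 20 + 3 = 23 weeks. The week-32 window is ±2 weeks, or 30 to 34.

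- Accepters at study week 32 have had 32 − 23 = 9 to 32 − 17 = 15 weeks of open-label drug, nominally 12. The nearest scheduled visit is therefore Week 12-A, which has its own label.
- Their off-drug visit, Week 32-A, falls nominally at 20 + 32 = 52 weeks from first dose.
- A decliner's week-20 record filed as week 32 would precede that window by at least 30 − 23 = 7 weeks, or 30 − 22 = 8 weeks on the 14-day window in Table 16-1.

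**Would decliners generate a week-32 efficacy record?** In Table 16-1, every item in the End of Study column except the exit form also appears in the Week 20 column. Section 7.1.7 adds the request for consent to the long-term follow-up protocol. What remains for a decliner to complete is therefore exit paperwork. On that reading sections 6.1 and 7.1.6 agree, and there is no second tape measurement to misfile.

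**What the model would do.** There are two broad ways to code time.

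1. *Visit as a factor, crossed with arm.* Week 32 then has a mean in one arm only, so no week-32 contrast can be estimated. With complete data, the contrasts at weeks 4, 12 and 20 are the differences in visit means, whether or not week 32 is in the file.
2. *One linear slope per arm.* Here week 32 matters. As an illustration only, assume sildenafil falls linearly to −20% at week 20. A least-squares line through weeks 0, 4, 12 and 20 gives a fitted 20-week change of −20.0%. Now add week 32 and assume the value holds at −20%. Mean time is 68/5 = 13.6, Sxx = 1584 − 5 × 13.6² = 659.2, and Sxy = −1200 + 5 × 13.6 × 11.2 = −438.4. The fitted change is 20 × (−438.4/659.2) = −13.3%. Assuming half rebound it is −7.7%, and assuming full rebound −2.1%.

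The second coding would distort the result, but the plan does not specify it. The percentages rest wholly on assumed values and are not an estimate of bias in this trial.

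**The case for a change.** The strongest case for a change is that the visit schedule shows who attends week 32 but does not say which records enter the model. For MRI the plan does write such a rule: section 10.2.1 names the post-placebo scan as the comparator for crossed-over subjects. Tape volume and the physician forms have no equivalent. Section 11 adds a responder analysis that uses several measurements on placebo patients without saying from which period. Section 10.2.2 also disagrees with other text. The synopsis ends the subject's assessment at 20 weeks, and section 7.4.4 keeps photographs taken outside baseline and week 20 out of the final analysis.

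The silence is real, and so are these mismatches. They do not establish the harm. Section 10.2.2 describes change from baseline, which is a within-subject quantity, and sets no arm against another. The faulty comparison appears only when its visit list is joined to section 7.4.3, the word volume there is read as tape volume, and time is coded as a slope. The tape reading is reasonable from context but not explicit. If MRI volume is meant, Table 16-1 has no week-32 scan and the issue disappears. The photograph mismatch affects weeks 4 and 12 as much as week 32, so it is a separate matter of scheduling.

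The obvious remedy has costs too. Ending the mixed model at week 20 would remove its within-subject use for off-drug change, which section 7.4.3 allows. Reporting week 32 in the sildenafil arm alone would leave out the Week 32-A values of crossed-over placebo subjects, who are seen off drug after a full active course.

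**Conclusion.** No change is needed. No untreated placebo value is scheduled at week 32, and the plan does not say where the between-arm comparison ends. But no stated rule produces a wrong result. The synopsis separates 20 weeks of evaluation on therapy from 12 weeks of follow-up off it. The section 7.1.7 heading, step 13 of section 7.1.6 and the -A labels all mark what comes after week 20 as a different phase. An analyst working from them would take between-arm contrasts through week 20 and summarise off-drug data within subjects.

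The reach of the gap is one of four post-baseline visits, for secondary measures, in a study that section 11 describes as exploratory and descriptive. The primary MRI endpoint and the visit-specific comparisons at weeks 4, 12 and 20 stand. The size of any bias cannot be computed, because the documents give no decline rate, no coding of time and no expected course on placebo.

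The conclusion assumes that the model treats visits separately, or stops at week 20 for the between-arm contrast, and that decliners' extra items are exit paperwork. If a single slope were fitted through week 32, the tape-volume comparison would not be interpretable.
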